- Occurrence of TEAEs (including TEAEs leading to death or discontinuation of treatment) in subjects with mRCC receiving M8891 combined with cabozantinib. Any AEs that occur

or worsen between start of study intervention and 30 days after end of study intervention will be considered TEAEs

- Study clinically relevant abnormal changes in clinical laboratory measures from baseline, vital signs, ECOG performance status, and ECGs from start of study intervention to 30 days after end of study intervention
- Objective Response according to RECIST v1.1 as assessed by Investigators

Secondary endpoints:

- Duration of Response (DoR) according to RECIST v1.1 criteria as assessed by Investigators
- PFS time according to RECIST v1.1 criteria as assessed by Investigators

Part 2B, Expansion Cohort

Primary endpoints:

- Occurrence of study serious AEs including deaths from first dose of study intervention to 30 days after end of study intervention
- Study clinically relevant abnormal changes in clinical laboratory measures from baseline, vital signs, ECOG PS, and ECGs from start of study intervention to 30 days after end of study intervention
- Occurrence of TEAEs (including deaths) from start of the study intervention to 30 days after end of the study intervention
- Objective response according to RECIST v1.1 criteria as assessed by Investigators

Secondary endpoints:

- DoR according to RECIST v1.1 criteria as assessed by Investigators
- PFS time according to RECIST v1.1 criteria as assessed by Investigators

Pharmacokinetics

Part 1, M8891 Single Agent, Solid Tumors

- PK parameters of M8891 after QD dosing, as applicable: C_{max} , t_{max} , AUC_{0-t} , $AUC_{0-\infty}$, $AUC_{0-\tau}$, $t_{1/2}$, λ_z , CL/F , CL_{ss}/F , V_z/F , $Racc(AUC_{\tau})$ and $Racc(C_{max})$

Part 2, M8891 Combined with Cabozantinib, mRCC

Part 2A, Dose Escalation

- PK parameters of M8891 in terms of C_{max} , t_{max} , AUC_{0-t} on Day 1 Cycle 1, (combined with cabozantinib, single dose)
- PK parameters of M8891 in terms of C_{max} , t_{max} , AUC_{0-t} on Day 8 and Day 15 Cycle 1, and Day 1 Cycle 2 (combined with cabozantinib, multiple dose)

- PK parameters of M8891 in terms of C_{max} , AUC_{0-t} , t_{max} , t_{lag} , $t_{1/2}$, $AUC_{0-\infty}$, CL/F , V_z/F on Day -1 Cycle 1 (M8891, single dose). **CCI**
- PK parameters of cabozantinib in terms of C_{max} , t_{max} , AUC_{0-t} on Day 1 Cycle 1 (combined with M8891, single dose)

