- Imaging analysis must be using the same technique during the study, e.g. it's not allowed to use CT scan at baseline then change to MRI during the study. Tumor response will be assessed, within 1 week prior to Day 1 of Cycles 3, 5, and 7, and every third cycle thereafter. Subjects who discontinue treatment will undergo EOT visit procedures.

Table 4

Schedule of Pharmacokinetic, Electrocardiogram Assessments and Food Guidance during Part 2A M8891 Combined with Cabozantinib, mRCC, Dose Escalation

Treatment Day	Time h (\pm min) ^{a,b}	ECG ^c	PK M8891	PK Cabozantinib
Day -1, C1	Pre-dose (-60 min)	X	X ^d	
	1 (\pm 5)		X ^d	
	2 (\pm 10)	X	X ^d	
	3 (\pm 15)		X ^d	
	4 (\pm 15)		X ^d	
	6 (\pm 15)	X	X ^d	
	8 (\pm 15)		X ^d	
D1 C1	Pre-dose (-60 min)	X	X	X
	1 (\pm 5)		X	
	2 (\pm 10)	X	X	X
	3 (\pm 15)		X	
	4 (\pm 15)		X	
	6 (\pm 15)	X	X	X
D8 C1	Pre-dose (-60 min)	X	X	X
	2 (\pm 5)	X	X	X
D15 C1	Pre-dose (-60 min)	X	X	X
	1 (\pm 5)		X	
	2 (\pm 10)	X	X	X
	3 (\pm 15)		X	
	4 (\pm 15)		X	
	6 (\pm 15)	X	X	X
D1C2	Pre-dose (-60 min)	X	X	X
	2 (\pm 10)	X	X	X
D1C3-5	Pre-dose (-60 min)	X		
	1 (\pm 5)	X		
D1C7 (and Day 1 of every third cycle)	Pre-dose (-60 min)	X		
	1 (\pm 5)	X		

C: Cycle; D: Day; ECG: Electrocardiogram; eCRF: Electronic case report form; mRCC: Metastatic renal cell carcinoma; PK: Pharmacokinetics.

a. At visits where assessment time points (ECG and PK) coincide with each other

- 1) Perform vital signs assessments at first
- 2) ECG assessments slightly before the specific collection time point
- 3) PK assessments at scheduled collection time point.

b. Actual collection times should be documented in the eCRF.

- c. Standard triplicate (within 2 min) 12-lead ECG will be obtained after the subject has been rested in semi-recumbent position for at least 5 min at the indicated times. ECGs will be also performed during the End of Treatment and Safety Follow-up Visit (30 ± 7 days). Triplicate ECGs will be read locally. The calculated QTcF interval average of the three 12-lead ECGs must be ≤ 450 ms for males and ≤ 470 ms for females for eligibility. Subjects, in which the calculated QTcF interval average increases to > 500 ms or > 60 ms change over baseline during treatment, must interrupt study treatment until further clinical evaluations (See Section 7.4.5).

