- d. All subjects in Part 2A will receive on Day -1, Cycle 1 a single dose of M8891 with a high calorie, high-fat breakfast. PK data collected at the indicated times will be compared with those obtained at the same dose-levels in Part 1 where subjects have received M8891 under fasted conditions.

Table 5

Schedule of Pharmacokinetic and Electrocardiogram Assessments during Part 2B M8891 Combined with Cabozantinib, mRCC, Expansion Cohort

Treatment Day	Time h (\pm min) ^{a,b}	ECG ^c	PK M8891	PK Cabozantinib
D1 C1	Pre-dose (-60 min)	X	X	X
	2 (\pm 10)	X	X	
	6 (\pm 15)	X	X	X
D8 C1	Pre-dose (-60 min)	X	X	X
	2 (\pm 5)	X	X	X
D15 C1	Pre-dose (-60 min)	X	X	X
	2 (\pm 10)	X	X	
	6 (\pm 15)	X	X	X
D1C2	Pre-dose (-60 min)	X		
	2 (\pm 5)	X		
D1C3-5	Pre-dose (-60 min)	X		
	1 (\pm 5)	X		
D1C7 (and Day 1 of every third cycle)	Pre-dose (-60 min)	X		
	1 (\pm 5)	X		

C: Cycle; D: Day; ECG: Electrocardiogram; eCRF: Electronic case report form; mRCC: Metastatic renal cell carcinoma; PK: Pharmacokinetics.

- a. At visits where assessment time points (ECG, and PK) coincide with each other
 - 1) Perform vital signs assessments at first
 - 2) ECG assessments slightly before the specific collection time point
 - 3) PK assessments at scheduled collection time point
- b. Actual collection times should be documented in the eCRF.
- c. Standard triplicate (within 2 min) 12-lead ECG will be obtained after the subject has been rested in semi-recumbent position for at least 5 min at the indicated times. ECGs will be also performed during the End of Treatment and Safety Follow-up Visit (30 \pm 7 days). Triplicate ECGs will be read locally. The calculated QTcF interval average of the three 12-lead ECGs must be \leq 450 ms for males and \leq 470 ms for females for eligibility. Subjects, in which the calculated QTcF interval average increases to $>$ 500 ms or $>$ 60 ms change over baseline during treatment, must interrupt study treatment until further clinical evaluations (See Section 7.4.5).

2 Sponsor, Investigators and Trial Administrative Structure

This clinical trial will be sponsored by EMD Serono Research & Development Institute, Inc., Billerica, MA, USA.

The Sponsor's legal representative in the EU is Merck KGaA, [name].

The Part 1 of the trial will be conducted at approximately 5 sites in USA. The Part 2 of the trial will be conducted at approximately 7 sites in USA.

The Coordinating Investigator **PPD**

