4.1.2 Secondary Objectives

Secondary objectives are:

- To evaluate the safety profile and tolerability of M8891 as a single agent
- To investigate the PK profile of M8891 as single agent
- To assess the antitumor activity of M8891 as single agent according to Response Evaluation Criteria in Solid Tumors (RECIST) v1.1
- To determine the recommend Phase II dose (RP2D) as single agent.

CCI

4.2

Part 2, M8891 combined with Cabozantinib, mRCC

In Part 2 of this study, M8891 combined with cabozantinib will be administered in subjects with mRCC.

4.2.1

Part 2A, Dose Escalation

Table 6

Part 2A Objectives and Endpoints

Objectives	Endpoints (Outcome Measures)

Primary
 
To determine the recommended dose for expansion (RDE) (MTD, if reached) of M8891 combined with cabozantinib in subjects with mRCC, based on safety, tolerability, and antitumor activity	
Occurrence of DLTs in subjects with mRCC receiving M8891 combined with cabozantinib during the first 22-day treatment cycle (21 days of M8891 combined with cabozantinib, preceded by 1 day of M8891 alone) based on predefined set of AEs.Occurrence of TEAEs (including TEAEs leading to death or discontinuation of treatment) in subjects with mRCC receiving M8891 combined with cabozantinib. Any AEs that occur or worsen between start of study intervention and 30 days after end of study intervention will be considered TEAEs.Study clinically relevant abnormal changes in clinical laboratory measures from baseline, vital signs, ECOG performance status, and ECGs from start of study intervention to 30 days after end of study interventionObjective response according to RECIST v1.1 as assessed by Investigators

Objectives	Endpoints (Outcome Measures)

Secondary
 
• To characterize the PK profile of M8891 (single and multiple dose exposure) combined with cabozantinib in subjects with mRCC• To further assess antitumor activity of M8891 combined with cabozantinib in subjects with mRCC	
• PK parameters of M8891 in terms of C_{max}, t_{max}, AUC_{0-t} on Day 1 Cycle 1, (combined with cabozantinib, single dose)• PK parameters of M8891 in terms of C_{max}, t_{max}, AUC_{0-t} on Day 8 and Day 15 Cycle 1, and Day 1 Cycle 2 (combined with cabozantinib, multiple dose)
CC1	

[figure not shown]

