Each part of the study will include a Screening period of up to 28 days, a study intervention period consisting of 21-day cycles of M8891 single agent (Part 1) and M8891 combined with cabozantinib (Part 2), an End of Study Intervention visit (within 7 days), and a Safety Follow-up period of 30 (\pm 7) days. Subjects who discontinue study intervention for any reason will complete the End of Study Intervention and Safety Follow-up visits. In Part 2A, before Cycle 1 of all dose levels, subjects will receive a single dose of M8891 in the morning in fed conditions (Day -1, Cycle 1) and the PK profile of M8891 will be evaluated pre-dose, 1, 2, 3, 4, 6, 8 and 24h (Day 1, Cycle 1) after administration (Section 5.1.3.2.1). Subsequently on Day 1 Cycle 1, subjects will initiate

treatment with M8891 combined with cabozantinib QD orally every morning under fasted conditions.

Study duration per subject is approximately 8 months for Part 1, and 12 months for Part 2 including screening, treatment and follow up.

[figure not shown]
The design of this study is presented in

Figure 1 and a detailed Schedule of Assessments (SoAs) is provided in Table 1, Table 2, Table 3, Table 4, and Table 5.

Figure 1

Study Design

AE: Adverse event; DL: Dose level; FBE Free-base equivalent; MTD: Maximum tolerated dose; QD: Once daily; SMC: Safety Monitoring Committee; RP2D: Recommended Phase 2 Dose; mRCC: metastatic renal cell carcinoma; **CCI** [REDACTED].

- a. The MTD of M8891 single agent will be defined, and RP2D of M8891 single agent suggested, by the SMC.
- b. Subjects should have progressed to 1 or more previous lines of systemic anticancer therapy, excluding treatment with cabozantinib.
- c. Cabozantinib will be given at the approved 60 mg FBE daily dosage with dosage adjustments to 40 mg or 20 mg permitted to manage AEs.

CCI [REDACTED]

CCI [REDACTED]

- f. 30 subjects evaluable for response.
- g. The DLT assessment period for Part 2A is the Cycle 1 (= 22 days, 21 days of M8891 combined with cabozantinib, preceded by 1 day of M8891 alone) of study treatment. The rest of the Cycles in Part 2A are 21-day cycles of M8891 combined with cabozantinib.
- h. See Section 8.5.1 for the Bayesian two-parameter logistic regression model.

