5.1.3.2 Part 2, M8891 combined with Cabozantinib, mRCC

5.1.3.2.1 Part 2A, Dose Escalation

In Part 2A, before Cycle 1 Day 1 of all dose levels, subjects will receive a single dose of M8891 in the morning in fed conditions (Day -1, Cycle 1) and the PK profile of M8891 will be evaluated. Subsequently on Day 1 Cycle 1, subjects will initiate treatment with M8891 combined with cabozantinib QD orally every morning under fasted conditions. Following Cycle 1, all other cycles will start with Day 1 and will include only the 21 days of M8891 combined with cabozantinib.

Subjects will accrue in cohorts of 3 subjects for evaluation of M8891 combined with cabozantinib 60 mg QD (with dosage adjustments to 40 or 20 mg FBE permitted to manage AEs as described in Section 6.5.5). Both drugs will be taken in the morning in fasted conditions. A Bayesian 2-parameter logistic regression model with overdose control will be used to assist the SMC with dose selection for the next cohort and to determine the MTD/RDE of M8891 combined with cabozantinib 60 mg QD for Part 2B.

Three pre-specified dose levels of M8891 are planned (20 mg, 35 mg and 60 mg) combined with 60 mg of cabozantinib. Dose levels may be added or skipped for others that are not part of the pre-specified set but they will never exceed the dose level of M8891 that has already been declared to be safe in Part 1. The dose levels have been chosen based on preliminary data from the ongoing Part 1 of the study. At the time of Amendment 2, M8891 single agent was being investigated at 60 mg QD in subjects with solid tumors. PK^{CC} studies have shown that the 20, 35 and 60 mg QD regimens reached pre-selected exposure (≥ 1500 ng/mL) at steady state while CCI

. Three and 5 Grade ≥ 3 TEAEs have been seen at 20 and 35 mg QD regimen, respectively. One DLT (Grade 4 thrombocytopenia) has been observed in the ongoing 60 mg QD cohort (Refer to the M8891 IB).

Dose escalation of the combination will proceed until the RDE of M8891 is reached in combination with a fixed dose of cabozantinib or dose escalation ends due to occurrence of an MTD, or the SMC decides ending dose escalation following review of safety, tolerability, and PK results, whatever occurs first. The maximum dose of M8891 combined with cabozantinib will not exceed the MTD of M8891 in monotherapy determined in Part 1 of the study.

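### Part 2A labels the Day 1 Cycle 1 M8891 parameters as single-dose, but Day 1 is the second M8891 dose, so any residual from Day -1 raises Cmax and AUC0-6 by an amount that depends on a half-life the documents do not give

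*Protocol*

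**What the plan says.** The Part 2A secondary PK objective in Table 6 (Section 4.2.1) and the Synopsis is "To characterize the PK profile of M8891 (single and multiple dose exposure) combined with cabozantinib in subjects with mRCC". The single-dose side of it is served by M8891 Cmax, tmax and AUC0-t "on Day 1 Cycle 1, (combined with cabozantinib, single dose"; the multiple-dose side by Days 8 and 15 and Cycle 2 Day 1. The Synopsis also lists Day -1 parameters, including a half-life, and labels those as single-dose M8891.

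Section 5.1.3.2.1 states that before Cycle 1 Day 1 "subjects will receive a single dose of M8891 in the morning in fed conditions". Footnote d of Table 4 confirms that this applies to everyone: "All subjects in Part 2A will receive on Day -1, Cycle 1 a single dose of M8891 with a high calorie, high-fat breakfast". Section 5.1 says the Day -1 profile is "evaluated pre-dose, 1, 2, 3, 4, 6, 8 and 24h (Day 1, Cycle 1) after administration", so its 24 h sample falls on Day 1. Then, per Section 5.1.3.2.1, "Subsequently on Day 1 Cycle 1, subjects will initiate treatment with M8891 combined with cabozantinib QD orally every morning under fasted conditions".

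Table 4 schedules M8891 samples on Day 1 and Day 15 before dosing and at 1, 2, 3, 4 and 6 h. Section 7.5.2 ends AUC0-t at the last quantifiable sample. No readable text subtracts residual drug.

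**The concern.** Two consecutive daily doses of one drug cannot both be single doses. The label is right on Day 1 for cabozantinib, which has its own line in the Synopsis, but the line at issue is for M8891.

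If the endpoint is followed as written, the report will present values containing Day -1 carry-over as single-dose exposure in combination. Two readings would then suffer:

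- **Accumulation.** A Day 15 to Day 1 ratio over 0-6 h would be too small, because its denominator already contains residual drug.
- **Cabozantinib effect.** A comparison with Part 1 Day 1, also fasted, could make carry-over look like an effect of cabozantinib on M8891. Section 3.3.3 expects almost no such effect, so a rise would stand out. The SMC reviews PK (Section 2) and may end Part 2A escalation partly on it (Section 5.1.3.4).

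**Working it through.** **Inputs from the documents.** The interval between the doses is 24 h (Section 5.1). Day 1 and Day 15 sampling ends at 6 h (Table 4), so AUC0-t is in effect AUC0-6. Day -1 appears to be a full dose: no reduced lead-in is described, and footnote d says "PK data collected at the indicated times will be compared with those obtained at the same dose-levels in Part 1".

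**Assumptions.** The documents state no half-life, accumulation ratio or carry-over figure, so there is nothing to reproduce. I assume a linear one-compartment oral model, absorption rate ka = 1 per hour, equal doses, and equal exposure fed and fasted. In units of dose over volume, with ke = ln 2 / t½:

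C(t) = ka/(ka − ke) × [exp(−ke·t) − exp(−ka·t)]

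Cmax inflation = max over 0-6 h of [C(t) + C(t + 24)] / max of C(t) − 1

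AUC inflation = AUC24-30 / AUC0-6, both for one dose

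| t½ (h) | Cmax, true single dose | Cmax, Day 1 | Inflation | AUC0-6 | AUC24-30 | Inflation |
|---|---|---|---|---|---|---|
| 2 | 0.570 | 0.570 | 0% | 2.337 | 0.001 | 0% |
| 4 | 0.693 | 0.706 | 2% | 3.306 | 0.071 | 2% |
| 6 | 0.754 | 0.808 | 7% | 3.766 | 0.306 | 8% |
| 12 | 0.840 | 1.064 | 27% | 4.323 | 1.345 | 31% |
| 24 | 0.900 | 1.366 | 52% | 4.646 | 2.836 | 61% |

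**Sensitivity.** With ka from 0.7 to 1.5 per hour, inflation passes 5% at a half-life of about 5 h, 10% at 6-7 h and 20% at 8-10 h. It scales with the Day -1 fed-to-fasted exposure ratio: at 8 h, AUC inflation is 15-18% with a ratio of 1 and about 11-27% with ratios of 0.7 to 1.5.

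**Effect on accumulation.** Let f be the AUC inflation and q = 2^(−24/t½). By Day 15 the 0-6 h AUC is about 1 + f/(1 − q) times the true single-dose value. At 12 h: 1 + 0.311/0.75 = 1.41. Dividing by the observed Day 1 value gives 1.41/1.311 = 1.08. At 24 h: 1 + 0.611/0.5 = 2.22, and 2.22/1.611 = 1.38.

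**Unmatched windows.** The Day -1 and Part 1 Day 1 profiles run to 24 h. The ratio (AUC0-6 + AUC24-30)/AUC0-24 is 3.376/5.662 = 0.60 at 4 h, 4.071/8.045 = 0.51 at 6 h, 5.668/12.719 = 0.45 at 12 h and 7.482/16.798 = 0.45 at 24 h. Set directly against those profiles, Day 1 AUC0-t would look too low.

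**Correction.** Subtract Cpre × exp(−λz·t), with Cpre from the Day 1 pre-dose sample and λz from Day -1. At 12 h, Cpre = 0.265 and the area removed over 0-6 h is 0.265 × (1 − 0.707)/0.0578 = 1.34, which matches AUC24-30 up to rounding. Under this model the bias goes.

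**The case against.** The best defence is that the label harms nothing that is planned. The objective is to characterise PK, and Section 8.5.4.1 analyses PK descriptively by dose level and day. The only cross-part comparison in the readable text is Day -1 against Part 1, and Day -1 has no carry-over. The schedule is disclosed, so a careful reader can take Day 1 to mean the first combined dose. Section 3.3.3 plans to monitor cabozantinib exposure and treats M8891 as an unlikely victim. Some PK text is redacted, and the supplied analysis plan (version 1.0, April 2018) predates Part 2 and says it will be amended if combination parts are added. A correction rule may therefore exist elsewhere.

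Much of this stands. No Day 1 interaction test is stated, absence of a correction can be asserted only for the readable text, and a short half-life would make the matter trivial. Linear superposition is also doubtful at 60 mg, where Section 3.3.1 reports exposure rising less than in proportion to dose. None of it makes the current label correct. A later analysis plan that followed the endpoint as written would still report Day 1 as single-dose M8891 exposure.

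**Conclusion.** The label is wrong for M8891, and the direction over a matched 0-6 h window is certain: any residual raises Day 1 Cmax and AUC0-6, provided the peak falls within 6 h. Whether the rise matters is not established. It runs from nothing at a half-life of 2 h to 52-61% at 24 h under the assumptions above.

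A reader might infer that single-dose exposure is materially overstated and that the trial is biased towards a false cabozantinib interaction. The documents do not support that, for three reasons. The half-life is missing. The interaction comparison is not stated. For AUC0-t compared without matching windows, the error runs the other way. A Day 1 versus Day -1 comparison is also confounded by food, since Day -1 is fed and Day 1 fasted. This is a minor point, worth correcting because the correction is nearly free.

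**What to change.** 1. Rename the endpoint in the Synopsis and Table 6 as first combined dose (second M8891 dose), and keep the single-dose label for Day -1.
2. In the Part 2 analysis plan, report Day 1 M8891 Cmax and AUC0-6 both uncorrected and with the decaying pre-dose residual subtracted as above. Flag subjects whose λz is unreliable. The Part 1 plan (SAP Section 16.1.2) asks for a regression window of at least twice the half-life. A terminal window of about 20-21 h within a 24 h profile supports half-lives up to about 10 h.
3. Use a common 0-6 h window for any cross-day or cross-part comparison, with fasted Part 1 Day 1 at the same dose level as the single-agent reference.

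The cost is one extra derivation. The Day 1 pre-dose sample and the Day -1 half-life are already planned, and dosing, visits and sampling do not change. The weakness is reliance on λz: the correction is least secure at half-lives above about 10 h, where the bias is largest, which is why both versions should be shown.

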
CCI

- j. Blood – ctDNA: at Day 1 pre-dose and during treatment pre-dose within 60 minutes prior to M8891 combined with cabozantinib treatment administration mandatory blood sampling (20 mL each) to assess mutant allele frequency of tumor-derived cell-free DNA.
- k. Imaging (e.g. CT scan) do not have to be repeated on Day -1, Cycle 1 if performed within 28 days as a screening/baseline assessment.
- l. Imaging analysis must be using the same technique during the study, e.g. it's not allowed to use CT scan at baseline then change to MRI during the study. Tumor response will be assessed within 1 week prior to Day 1 of Cycles 3, 5, and 7, and every third cycle thereafter. Subjects who discontinue treatment will undergo EOT visit procedures.

Table 3

Schedule of Assessments for Part 2B, M8891 Combined with Cabozantinib, mRCC, Dose Expansion

Activity / Assessment	Screening	On Treatment Visits							EOT ^a	Safety F/U ^b	Notes
		M8891 + Cabozantinib									
			Cycle 1	Cycle 2-4	Cycle 5	Cycle 7 and on					
Cycle Day	-28 to -1	1	8	15	1	15	1	1 of every third cycle	Within 7 days of last intervention	30 days after last dose	After Cycle 7, visits on Day 1 of every third cycle For rescreening see Section 5.1.1
Visit Window			±1	±1	±2	±2	±3	±3	+7	±7	
Written informed consent	X										
Demography	X										
Medical history	X										
Serum pregnancy test (beta hCG) ^c	X										
Physical examination	X ^d	X	X	X	X	X	X	X	X		
Vital signs, weight, height (height at screening only)	X	X	X	X	X		X	X	X		Heart rate, diastolic and systolic blood pressure, respiratory rate, body temperature
12-lead ECG	X	X	X	X	X		X	X	X		Table 5
ECOG PS	X	X	X	X	X	X	X	X	X		
AE assessment	X	X	X	X	X	X	X	X	X	X	AE and concomitant medication assessment should be performed at every visit
Concomitant medication	X		X	X	X	X	X	X	X		
Hematology, biochemistry, coagulation, thyroid function ^e , urine chemistry, serology ^f	X ^d	X	X	X	X	X	X	X	X		Appendix III
Urine pregnancy test		X		X		X	X	X			Appendix III
Archival tumor biopsy (if available) ^g	X										
Blood – PK blood sample/s M8891		X	X	X							Table 5 PK samples will be collected only until Day 15 Cycle 1
Blood – PK blood sample/s cabozantinib		X	X	X							Table 5 PK samples will be collected only until Day 15 Cycle 1

Activity / Assessment	Screening	On Treatment Visits							EOT ^a	Safety F/U ^b	Notes
		M8891 + Cabozantinib									
			Cycle 1	Cycle 2-4	Cycle 5	Cycle 7 and on					After Cycle 7, visits on Day 1 of every third cycle

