	
pressure sensitive areas of hands and feet, and use of thick cotton gloves and socks to prevent injury and to keep the palms and soles dry.
 
 Subjects with skin disorders should be carefully monitored for signs of infection (e.g., abscess, cellulitis, or impetigo). Early signs of hand-foot syndrome could be tingling, numbness, and slight redness or mild hyperkeratosis. Early manifestations include painful, symmetrical red and swollen areas on the palms and soles. The lateral sides of the fingers or peri-ungual zones may also be affected. Adequate interventions are required to prevent worsening of skin symptoms such as blisters, desquamations, ulcerations, or necrosis of affected areas. Aggressive management of symptoms is recommended, including early dermatology referral. In the case of study treatment-related skin changes (e.g., rash, hand-foot syndrome), the Investigator may request that additional assessments be conducted with the subject's consent. These assessments may include digital photographs of the skin changes and/or a biopsy of the affected skin and may be repeated until the skin changes resolve. VEGF inhibitors can cause wound healing complications and wound dehiscence which may occur even long after a wound has been considered healed. Therefore, surgical and traumatic wounds must have completely healed prior to starting study treatment and be monitored for wound dehiscence or wound infection while the subject is being treated with M8891 with cabozantinib. 								
Hypertension	
 Hypertension is a common class effect of drugs that inhibit VEGF pathways. Blood pressure should be monitored in a constant position at each visit (either sitting or supine). In general, subjects with known hypertension should be optimally managed prior to study entry. Decisions to decrease or hold the dose of study treatment must be based on blood pressure readings taken by a medical professional and must be confirmed with a second measurement at least 5 minutes following the first measurement. Other than for hypertension requiring immediate therapy, the presence of new or worsened hypertension should be confirmed at a second visit before taking therapeutic action. It is recommended that this second visit occurs within 1 week. In the case of hypertensive crisis or hypertensive encephalopathy, study treatment should be discontinued. 								

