Thromboembolic Events	
 Study treatment should be discontinued in subjects who develop PE or DVT, an acute myocardial infarction or any other clinically relevant arterial thromboembolic complication (Section 5.5). 								
Proteinuria	
 During each safety assessment visit, proteinuria will be quantified by measuring the urine protein-to-creatinine (UPCR) ratio. In addition, urine dipstick analysis will be performed (see Table 2 and Table 3). 
  
 Severity of Proteinuria (UPCR)	Action To Be Taken	
   
 1 mg/mg (\leq 113.1 mg/mmol)	 
 No change in study treatment or monitoring 	
 
 > 1 and $<$ 3.5 mg/mg ($>$ 113.1 and $<$ 395.9 mg/mmol)	 
 No change in study treatment required Consider confirming with a 24-hour protein assessment within 7 days 	
 
 \geq 3.5 mg/mg (\geq 395.9 mg/mmol)	 
 Repeat UPCR within 7 days and once per week. If UPCR $<$ 1 on 2 consecutive readings, UPCR monitoring can revert to protocol-specific times. (Second reading is confirmatory and can be done within 1 week of first reading.) Hold study treatment pending repeat UPCR within 7 days and/or 24-hour urine protein. If \geq 3.5 on repeat UPCR, continue to hold study treatment and check UPCR every 7 days. If UPCR decreases to $<$ 2, 	
  
	Severity of Proteinuria (UPCR)	Action To Be Taken	1 mg/mg (\leq 113.1 mg/mmol)	
 No change in study treatment or monitoring 	> 1 and $<$ 3.5 mg/mg ($>$ 113.1 and $<$ 395.9 mg/mmol)	
 No change in study treatment required Consider confirming with a 24-hour protein assessment within 7 days 	\geq 3.5 mg/mg (\geq 395.9 mg/mmol)	
 Repeat UPCR within 7 days and once per week. If UPCR $<$ 1 on 2 consecutive readings, UPCR monitoring can revert to protocol-specific times. (Second reading is confirmatory and can be done within 1 week of first reading.) Hold study treatment pending repeat UPCR within 7 days and/or 24-hour urine protein. If \geq 3.5 on repeat UPCR, continue to hold study treatment and check UPCR every 7 days. If UPCR decreases to $<$ 2,

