7.4.4 Vital Signs, Physical Examinations, and Other Assessments

Vital sign, physical exam, and other assessments include: heart rate, diastolic blood pressure systolic blood pressure, weight, temperature, and additional assessments as included in Table 1, Table 2, and Table 3.

For timings of assessments, see the SoAs (Table 1, Table 2, and Table 3). For detailed procedures refer to the Manual of Operations.

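### Table 3 leaves blood pressure unscheduled at Day 15 of Cycles 2–4 in Part 2B, while Table 12 asks for it at every visit

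*Protocol*

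**What the plan says.** **Table 3, Part 2B schedule.** The row "Vital signs, weight, height (height at screening only" is marked at Screening, at all three Cycle 1 visits, at Day 1 of Cycles 2–4, at Cycle 5 Day 1, from Cycle 7 onward and at EOT. It is blank at Day 15 of Cycles 2–4 and at safety follow-up. Its Notes cell defines the content of the row: "Heart rate, diastolic and systolic blood pressure, respiratory rate, body temperature".

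**Other rows at the same visit.** Physical examination, ECOG PS, adverse events, concomitant medication and the laboratory row (which includes urine chemistry) are all marked at Day 15 of Cycles 2–4. The Notes column adds "AE and concomitant medication assessment should be performed at every visit".

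**Table 12 (Section 6.5.5), hypertension entry.** "Blood pressure should be monitored in a constant position at each visit (either sitting or supine". On dosing it states: "Decisions to decrease or hold the dose of study treatment must be based on blood pressure readings taken by a medical professional". The table is for M8891 given with cabozantinib, so it applies to Part 2B.

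**Table 12, proteinuria entry.** "During each safety assessment visit, proteinuria will be quantified by measuring the urine protein-to-creatinine (UPCR) ratio".

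**Section 7.4.4.** "For timings of assessments, see the SoAs (Table 1, Table 2, and Table 3".

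**Part 2B primary endpoints (Synopsis and Table 7).** These include "Study clinically relevant abnormal changes in clinical laboratory measures from baseline, vital signs, ECOG PS, and ECGs from start of study intervention".

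The SAP covers only the monotherapy dose escalation and does not bear on this point.

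**The concern.** Two parts of the same protocol give sites different instructions for a safety measurement. Table 12 wants a reading at every visit. The operative schedule, to which Section 7.4.4 refers for timing, omits it at three visits when the subject is already in clinic. These are the only on-treatment visits in Table 3 without a vital signs mark.

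The measurement matters for this regimen. Table 12 treats hypertension as a familiar effect of VEGF-pathway inhibitors and ties dose reductions and holds to readings made by a medical professional. A clinic visit is where such a reading can be made. Vital-sign changes also sit among the Part 2B primary endpoints, so the blank removes data from a listed endpoint as well as from subject management.

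**Working it through.** The plan gives no figure to reproduce. The check compares tables and counts visits.

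**1. Is the blank real, or a fault in reading the table?** In Table 3 the 12-lead ECG row is blank in the same column. Table 5, which sets the Part 2B ECG times, lists no Day 15 ECG after Cycle 1, so the ECG blank is correct and the columns line up. The later marks and the Notes text in the vital signs row also fall in the right place. The blank is therefore taken as real.

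**2. Does it look intended?** The marks at Day 15 of Cycles 2–4 are:

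| Row | Table 2 (Part 2A) | Table 3 (Part 2B) |
|---|---|---|
| Physical examination | X | X |
| Vital signs | X | blank |
| 12-lead ECG | blank | blank |
| ECOG PS | X | X |
| Laboratory tests, including urine chemistry | X | X |

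Table 5 supports the missing ECG. No text was found that supports dropping blood pressure. Table 12's other per-visit request, the urine protein-to-creatinine ratio, is carried at this visit through the urine chemistry mark (Appendix III lists UPCR under urine chemistry).

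**3. Visit count.** With 21-day cycles, nominal day = (cycle − 1) × 21 + cycle day.

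- Cycle 1: Days 1, 8, 15
- Cycle 2: Days 22, 36
- Cycle 3: Days 43, 57
- Cycle 4: Days 64, 78
- Cycle 5 Day 1: Day 85

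That is 3 + 2 + 2 + 2 + 1 = 10 visits. Vital signs are marked on Days 1, 8, 15, 22, 43, 64 and 85, which is 7. They are blank on Days 36, 57 and 78, which is 3. Urine chemistry is marked at all 10.

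**4. Gaps between readings, Day 22 to Day 85.**

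- Table 3 as written: Days 22, 43, 64, 85, so 4 readings with gaps of 21, 21 and 21 days.
- With Day 15 added: Days 22, 36, 43, 57, 64, 78, 85, so 7 readings with gaps of 14, 7, 14, 7, 14 and 7 days.

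The longest nominal gap falls from 21 to 14 days.

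**5. Later gaps.** Cycle 5 Day 1 to Cycle 7 Day 1 is 2 × 21 = 42 days, and every third cycle thereafter is 3 × 21 = 63 days. Table 3 has no clinic visit inside those intervals, so they do not conflict with a per-visit instruction and are not part of this point.

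**The case against.** The case for leaving the table alone is mainly about weight.

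- **Table 12 already asks for the reading.** A site that follows it takes blood pressure at Day 15 and the difference is zero. This stands, and it limits the consequence to sites that work from the schedule.
- **It could be a hierarchy, not a conflict.** Section 7.4.4 gives timing to the schedules, while Table 12 is headed as management recommendations and uses advisory wording. Part 2B is also lighter than Part 2A in other respects (no Day -1, sparser PK sampling). The documents do not rule this reading out. But on this reading a site following the schedule still has no planned reading at a visit where Table 12 wants one, and no text gives a reason for that.
- **Physical examination is marked that day.** Sections 7.4.4 and 8.5.5 group vital signs with physical examination, so many sites would take blood pressure anyway. That makes omission less likely. It does not fill the cell, because Table 3 keeps separate rows and names blood pressure only in the vital signs row.
- **The protein-to-creatinine comparison is imperfect.** The laboratory row is composite, and the same Table 12 entry promises a urine dipstick for which neither Table 2 nor Table 3 shows a visible row. So Table 3 does not mirror Table 12 reliably. The comparison is supporting evidence only; the conflict over blood pressure does not depend on it.
- **The consequence is small.** Blood pressure is still marked throughout Cycle 1, at Day 1 of Cycles 2–5 and at EOT, the endpoint is analysed descriptively, and longer gaps occur later by design. All true. Nor does the point rest on the confirmation visit that Table 12 recommends for hypertension, since a raised Day 1 value needs that under either schedule.

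**Conclusion.** The inconsistency is real and narrow. It concerns one measurement, blood pressure, at three scheduled visits per Part 2B subject. For a site following Table 3 alone, readings from Cycle 1 Day 1 through Cycle 5 Day 1 number 7 instead of 10, and the longest gap from Day 22 to Day 85 is 21 days instead of 14. For a site following Table 12 there is no loss. No sample size, error rate, estimate or decision rule is affected, and no missed event is demonstrated.

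The figures assume nominal visit days with windows ignored, and a subject who stays on treatment to Cycle 5 Day 1. Whether the blank was deliberate cannot be settled from the documents; the Part 2A schedule and the absence of any stated reason suggest that it was not. The point is worth correcting because the toxicity is expected, dose holds depend on clinic readings, and the subject is already in clinic.

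**What to change.** In Table 3, mark vital signs, or at minimum blood pressure, at Day 15 of Cycles 2–4, so that it agrees with Table 12 and with Table 2.

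The cost is one cell in one table and one short measurement at up to three existing visits per subject. No new visit is needed. If the sponsor does intend fewer readings in Part 2B, Table 12 should say so, so that sites have a single instruction.
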